5.5 Preparation and Method of Administration

Each bottle of *Octagam 10%* must be examined visually by the pharmacist or designee for particulate matter and discoloration prior to pooling. Non-homogenous solutions or those that have a deposit must not be pooled. The same procedures should be performed also for placebo.

The preparation of IMP should be performed under aseptic conditions preferably using a sterile bench, as described in the manual handed out to the hospital pharmacist or designee. IMP administration should be completed no later than 8 hours after preparation.

The *Octagam 10%* must be allowed to warm to room or body temperature prior to IMP administration. The same holds true for placebo for subjects in the placebo arm.

Subjects must be monitored before infusion and carefully observed for any symptoms at least once throughout the infusion period and at least 1 hour thereafter.

5.6 Blinding, Emergency Envelopes, and Breaking the Study Blind

The Investigators will be provided with an unblinding procedure to disclose the actual treatment of a particular subject in case of medical emergency; this can be a sealed envelope or its electronic equivalent.

To maintain blinding, infusions will be administered using blinded infusion over pouches and sites may opt to also use opaque or covered infusion lines. The blinded label will be fixed onto the infusion bag as well as to the opaque over pouch by the unblinded hospital pharmacist or designee. An over pouch (normally used for light protection) will be put over the infusion bag to maintain blinding. The new labels will be identical for both *Octagam 10%* and placebo, so that the content of the bags is only known to the unblinded hospital pharmacist or designee.

The unblinded pharmacist or designee will prepare and send the blinded infusion bag(s) per subject (and potentially with the opaque infusion line) to infusion center for administration.

To further assure the double-blind character of this study, the Investigator or designee who administers the medication to the subject will not be involved in any other evaluations other than drawing blood samples or checking for vital signs.

Breaking the blind in individual subjects during the double-blind study is permitted only in case of a SAE or unexpected ADR when knowing the type of the administered IMP is required for therapeutic decisions regarding this event to be taken.

A designated unblinded statistical team not otherwise involved in the study is unblinded to create randomization materials and provide the IDMC with unblinded study results as described in the IDMC charter and Statistical Analysis Plan (SAP).

Additional information on analysis timing and unblinded analyses can be found in Section 9.2.1.

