3.1 Primary and Secondary Endpoints

3.1.1 Primary Endpoint

- Proportion of subjects with stabilized or improved clinical status at Day 7 of at least one category on a 6-point clinical status scale.

Clinical status categories will be defined as:

1. Hospital discharge or meet discharge criteria (discharge criteria are defined as clinical recovery, ie, no fever, respiratory rate, oxygen saturation return to normal, and cough relief).
2. Hospitalization, not requiring supplemental oxygen.
3. Hospitalization, requiring supplemental oxygen (but not non-invasive mechanical ventilation (NIV)/high-flow nasal cannula [HFNC]) as defined by A-a Gradient <150 mmHg.
4. ICU/hospitalization, requiring NIV/HFNC therapy, as defined by A-a Gradient \geq 150 mmHg.
5. ICU, requiring extracorporeal membrane oxygenation (ECMO) and/or IMV.
6. Death.

A subject meets the success criteria of stabilization or improvement if the clinical status category on Day 7 is not worse than the clinical status category at Baseline (Day 1 prior to IMP infusion).

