The subject will receive either *Octagam 10%* medication in the dose of 2 g/kg administered over 4 days (0.5 g/kg/day), or an equivalent volume of placebo (saline), infused slowly over approximately 2 hours per day over 4 consecutive days. Note: Subjects must be monitored before infusion and carefully observed for any symptoms at least once throughout the infusion period and at least 1 hour thereafter.

The following activities/assessments will be performed on **Day 1 through Day 4**:

1. Infusion of IMP according to randomization code: *Octagam 10%* or placebo
2. Vital signs (taken once during and again after infusion)
3. SpO₂ saturation (see Section 7.2.4)
4. Post-infusion site assessment
5. Modified Borg Dyspnea Scale
6. MQoL-SIS
7. AE monitoring
8. Concomitant medication use review and documentation

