9.3 Randomization, Stratification, and Code Release

Each eligible subject will be randomized to either the treatment (IVIG) or placebo groups by study site. The randomization will be conducted using permuted blocks with block size randomly selected in each site stratum. A randomization statistician, not otherwise involved in the study, will generate the randomization list using a validated randomization program and deliver the allocation schedule to the unblinded study pharmacist in a secure and confidential manner. For Russia and Ukraine, this will be delivered with the help of the interactive response technology system. The pharmacist at the dispensing site will be unblinded to treatment and is responsible for blinding the study drug so that the infusion nurse, subject, and other study staff remain blinded to treatment. Moreover, since the pharmacist is not involved in the recruitment or management of subject, allocation concealment will be preserved. The process of blinding the study drug will be described in detail in another study supporting document.

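### Section 5.6 covers the bag to protect the blind but leaves opaque or covered infusion lines to each site, so the fluid may be visible at the bedside

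*Protocol*

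**What the plan says.** Protocol Section 5.6 sets two levels of masking. For the bag the rule is firm: "An over pouch (normally used for light protection) will be put over the infusion bag to maintain blinding", with identical labels for both products. For the tubing it is permissive: "infusions will be administered using blinded infusion over pouches and sites may opt to also use opaque or covered infusion lines". The same section has the unblinded pharmacist send the masked bag for infusion "and potentially with the opaque infusion line", so supply of the opaque line is also conditional.

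Section 5.6 adds a second safeguard. The person who gives the infusion "will not be involved in any other evaluations other than drawing blood samples or checking for vital signs".

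Section 9.3 states the aim. The pharmacist blinds the drug "so that the infusion nurse, subject, and other study staff remain blinded to treatment", and a separate supporting document is to describe how. Section 5.2 refers to a study-specific pharmacy manual. Its master labels describe the products as 100 mg protein per mL and 0.9% sodium chloride.

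Nothing in the protocol or the SAP requires a covered line, and neither plans a check of whether the blind held.

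**The concern.** The protocol covers the bag expressly to keep the blind, so it treats the contents as something that might be recognised. The same fluid then runs through tubing beside the subject, and at a site that does not opt in nothing hides it. The aim in Section 9.3 covers nurse, subject and other staff, yet the mandatory measures in Section 5.6 mask only the bag.

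If treating staff or the investigator could tell the arms apart, several outcomes that depend on their judgement could shift:

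- **Time to discharge.** This is the first key secondary, and under SAP Section 14 the hierarchy stops at the first non-significant test. A distorted result here would open or close the path to the other five.
- **Time to recovery, time to first improvement and proportion improved.** These depend on bedside decisions to reduce oxygen or discharge.
- **Escalation of oxygen support.** This bears on categories 3 and 4.
- **Adverse events.** They are elicited by questioning, and the investigator judges causality.

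Because covering is a site option, the exposure could also differ between sites.

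**Working it through.** The point rests mainly on text. Arithmetic applies to the length of exposure and to one illustration.

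**1. What is required.** Bag: covered at every site. Line: covered if the site chooses. Drip chamber: not mentioned. Intended scope of the blind: infusion nurse, subject and other staff.

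**2. How long the line may be in view.** Inputs are from Protocol Section 5.4: 0.5 g/kg/day for 4 days, with rates of 0.01, 0.02 and 0.04 mL/kg/min. The product is 10%, that is 0.1 g/mL.

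- Daily volume: 0.5 / 0.1 = 5 mL/kg.
- First 30 min: 0.01 × 30 = 0.3 mL/kg.
- Next 30 min: 0.02 × 30 = 0.6 mL/kg.
- Remainder: 5 − 0.3 − 0.6 = 4.1 mL/kg, which takes 4.1 / 0.04 = 102.5 min.
- Total: 30 + 30 + 102.5 = 162.5 min, about 2.7 h per infusion.
- Four infusions: 4 × 162.5 = 650 min, about 10.8 h.

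Elsewhere the protocol gives about 2 hours per infusion, so 4 × 2 = 8 h. The duration and the rates do not agree and those passages should be reconciled; I take no view on which is right and use 8 to 10.8 h as the range. Section 5.4 allows slower infusion in some subjects, which would lengthen it. This is time with a line running, not time under observation: Section 5.5 asks staff to observe the subject at least once during the infusion and for at least 1 hour afterwards.

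**3. Which endpoints are open to influence.**

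- Primary (Day 7). Success means no worse a category than at baseline. Subjects enter on supplemental oxygen and not on invasive ventilation, so baseline is expected to be 3 or 4. For a baseline of 3, the closest contrast is 3 versus 4. It involves a bedside decision on support, but Section 7.2.4 requires an A-a gradient from arterial blood gas at Day 1 and, for status 3 or 4, at Day 7. Categories 5 and 6 are ECMO or invasive ventilation, and death. Protection is therefore partial but real.
- Day 14 stabilisation. Section 7.2.4 schedules the A-a gradient only for Day 1 and Day 7, so this anchor is absent.
- Discharge, recovery and improvement. No comparable blood-gas anchor after Day 7.
- Dyspnea and quality-of-life scales. Completed on infusion days, but exploratory and not tested (SAP Section 15).

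**4. Illustration only.** Suppose there is no true effect, 104 per arm, a common success rate p of 0.6 to 0.8, and a net assessment bias b added to the IVIG rate. The value of b is assumed; nothing in the documents gives it. The chance of a significant result favouring IVIG is

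Φ[(b − 1.96 × √(2·p̄(1−p̄)/n)) / √((p₁(1−p₁)+p₂(1−p₂))/n)], with p₁ = p, p₂ = p + b and p̄ their mean.

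For p = 0.6 and b = 0.05: (0.05 − 1.96 × 0.0671) / 0.0670 = −1.22, so 11.2%.

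| b | p from 0.6 to 0.8 |
|---|---|
| 0 | 2.5% |
| 0.02 | 4.8–5.6% |
| 0.05 | 11.2–15.6% |
| 0.10 | 32.6–52.4% |

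This shows why a small avoidable bias is worth removing. It does not estimate the effect of an uncovered line.

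**The case against.** The strongest reply is that recognisability in tubing is inferred. Neither document describes the colour or foaming of either fluid, and a pouch over a bag does not prove that a narrow line would reveal the arm. The supporting blinding document and the pharmacy manual were not available and may already require covers. Both points stand, and they are why this is a risk and not a finding that the blind failed. They do not remove the inconsistency in the protocol, which treats masking as necessary for the bag and optional for the line.

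A reader might also infer that, because the administrator may still check vital signs, that person's readings decide the primary endpoint. The documents do not support this:

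- Infusions are on Days 1 to 4, and the primary assessment is on Day 7. Infusion-day readings do not set the Day 7 category, apart from values carried forward or early discharge.
- The discharge criteria ("no fever, respiratory rate, oxygen saturation return to normal", plus cough relief) define category 1. For a baseline of 3 or 4, categories 1 and 2 are both successes.
- Whether vital signs in Section 5.6 include SpO₂ is unclear. Section 7.3.1 groups them, Section 7.3.5 leaves SpO₂ out, and Section 6.1.2 lists the two separately.
- SpO₂ on Days 1 to 4 is read before that day's infusion, so the baseline value precedes any exposure.

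Finally, the SAP reports accelerated enrolment and a data review at 50% of subjects enrolled. A change to Section 5.6 cannot protect infusions already given. That limits the benefit but does not answer the point.

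**Conclusion.** The point holds as a design weakness that is cheap to correct. Section 5.6 leaves one visible part of the infusion system unmasked unless the site decides otherwise, while Section 9.3 relies on everyone at the bedside staying blinded. Potential exposure is about 8 to 10.8 hours of running line per subject at any site that does not opt in.

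It rests on two assumptions: that the fluids can be told apart in clear tubing, and that the unseen manuals do not already require covers. If either fails, the concern falls away or becomes a matter of wording.

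The most serious confirmatory consequence is for time to discharge, through treating staff or the investigator seeing the line. The primary endpoint is less exposed, for the reasons given above. The documents do not say how many of the approximately 20 sites would cover lines, so no count of affected subjects can be given. Nor do they support a claim that any subject was unblinded.

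**What to change.** In Protocol Section 5.6, replace the clause "sites may opt to also use opaque or covered infusion lines" with a requirement that the line and drip chamber be opaque or covered for every infusion, in both arms and at all sites. In the sentence on what the pharmacist sends, delete *potentially* from "and potentially with the opaque infusion line". Align the pharmacy manual with the new text; if it already requires covers, the protocol wording should say so.

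The cost is the covers or opaque lines, which the protocol already foresees. The small downside is that line faults are slightly harder to see. For infusions given before the change, the study report could state which sites had used covers.

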5.2 Packaging and Labelling

5.2.1 For the US sites

Octagam 10% delivered as ready-to-use solution in glass bottles; commercially labeled product will be provided to the clinical study sites. Appropriately trained study staff may over-label the commercial supplies with an investigational product label, provided by the Sponsor, that will meet all FDA requirements under 21 CFR 312.6 and shall include the statement: **Caution: New Drug—Limited by Federal (or United States) law to investigational use**, as permitted in accordance with local Standard Operating Procedures (SOPs). Investigational product labels will also be provided for placebo supplies that will be sourced from the site pharmacy's commercial supplies.

After transfer and pooling into Polyvinyl Chloride-free, Diethylhexylphthalate-free and latex-free, infusion bags, the medication (*Octagam 10%* or placebo) will be blinded with an over pouch and re-labeled (both the infusion bag [as permitted in accordance with local SOPs] and the over pouch). The over-label for the infusion bags and over pouches will also include the 21 CFR 312.6 required statement: **Caution: New Drug—Limited by Federal (or United States) law to investigational use**.

Instructions for over-labeling both *Octagam 10%* and saline with investigational product labels will be provided in a study-specific pharmacy manual.

US Master Label – Octagam 10%:

Caution: New Drug-Limited by Federal (or United States) law to investigational use	
Study: GAM10-10	
Octagam 10%	Unit size: _____ mL
1 mL contains: 100 mg protein of which 96% is human normal immunoglobulin. Infusion solution for intravenous administration.	
To be stored at +2°C (36°F) to +8°C (46°F) and protected from light. Must not be frozen. Must be inspected visually for particulate matter and discoloration prior to administration. Do not use non-homogenous solutions or those that have a deposit.	
To be warmed up to room or body temperature before use.	
Dosage: refer to Clinical Study Protocol, Section 5.4	
Patient no.: _ _ _ _ _ _ _ _	Visit no.: _ _ _
Infusion Day: _ _ _	
Sponsor: Octapharma USA, INC. [name] [REDACTED]	
[REDACTED]	
Batch no.: _____	Expiration date: _____

US Master Label – Saline:

Caution: New Drug-Limited by Federal (or United States) law to investigational use	
Study: GAM10-10	
Sodium Chloride 0.9% w/v solution	Unit size: _____ mL

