7.3.4 Laboratory Safety Evaluations

The following laboratory parameters will be investigated during the study at the time points specified in Table 1: Flow Chart of Assessments and below.

All laboratory assessment will be performed at the local laboratories for each study site. In Russia and Ukraine, a central local laboratory could be used for all or part of the tests depending on the site facilities. Samples will be drawn prior to IMP infusions on Day 1 through Day 4, if appropriate:

Laboratory Measures at Screening:

- Comprehensive Metabolic Panel (CMP)
- Complete blood count (CBC) with differential
- D-Dimer
- Fibrinogen
- Prothrombin time (PT), partial thromboplastin time (PTT), international normalized ratio (INR)
- hsCRP
- Erythrocyte sedimentation rate (ESR)
- Ferritin, lactic acid dehydrogenase (LDH)
- Cytokines (IL-1Beta, IL-6, TNF-alpha, IFN-gamma)
- C3, C4, CH50
- Total CK, CK-MB fraction, myoglobin
- High sensitivity Troponin I (hs-cTnI) or cTnI-ultra
- Serum pregnancy
- Blood culture
- Urine legionella, pneumococcal antigens

Laboratory measures for Day 1 through Day 3 (If less than 8 hours between Screening lab draw and Baseline Day 1, Baseline labs do not need to be redrawn):

- BUN
- Serum creatinine
- Sodium
- Potassium
- D-Dimer
- Arterial Blood Gases (Day 1 only)

Laboratory measures for Day 4:

- BUN
- Creatinine
- Sodium
- Potassium
- PT, PTT, INR
- CBC with differential
- D-Dimer

Laboratory measures for Day 7:

- CMP
- ESR
- Fibrinogen
- PT, PTT, INR
- CBC with differential
- hsCRP
- D-Dimer
- Ferritin, LDH
- Arterial Blood Gases (for patients with a clinical status of 3 or 4)

Laboratory measures for Day of Discharge (only if discharge is after Day 7) or Day 33, whichever is sooner:

- CMP
- CBC with differential

- hsCRP
- Cytokines (IL-1Beta, IL-6, TNF-alpha, IFN-gamma)
- C3, C4, CH50
- Total CK, CK-MB fraction, myoglobin
- D-Dimer
- Ferritin, LDH
- High sensitivity Troponin I (hs-cTnl) or cTnl-ultra
- PT, PTT, INR
- Fibrinogen

The methods of determination and normal ranges for each parameter will be provided in the clinical study report.

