9.1 Determination of Sample Size

A subject is determined to reach the primary endpoint “stabilization or improvement in clinical status defined as maintenance or improvement by one category on a 6-category clinical status scale on Day 7” if the clinical status category on Day 7 is not worse than the clinical status category at Baseline (Day 1 prior to IMP infusion).

The study is determined to be successful if the proportion of subjects randomized to the IVIG group who reach the primary endpoint is significantly greater than the proportion of subjects randomized to the placebo group who reach the primary endpoint.

High-dose IVIG is used as a therapeutic option for severe-type COVID-19 (37) and given the severity of the population in our study as compared to the reference study, we assume 80% of subjects in the IVIG group and 60% of subjects in the placebo group will meet the primary endpoint.

With overall two-sided significance level of 0.05 when testing the difference in proportions between two treatment groups using normality approximation, 176 subjects (n=88 for each treatment group) will provide statistical power of at least 80%. Assuming a drop-out rate of 15% from Baseline (Day 1) relative to the efficacy assessment date at Day 7 after first dose for both groups, a final sample size of 208 (n=104 for each treatment group) is sufficient to maintain the minimum statistical power as 80%.

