### 7. Blinded Data Review

Prior to scheduled study unblinding, the data will be reviewed in a blinded fashion for final data analysis decisions. Based on analysis needs, the lead statistician will develop specific listings for this review and will document decisions made prior to unblinding. These decisions may include (but not necessarily be restricted to) protocol violations leading to inclusion/exclusion of subjects in the different analysis populations and/or data points in specific analyses. More specifically, protocol violations will include those documented in the protocol violation CRF as well as violations that can be detected directly from the data base. Decisions on missing data, identification of prohibited medications and final imputation of endpoints will be done during this blinded review phase. Blinded data review may also include clinical evaluation of safety data for reasonableness or to issue clinical queries to the site if needed. Any decisions affecting the analysis will be described in internal documentation and the clinical study report.

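### No blinding control covers post-infusion laboratory results, so protein values could reveal the arm to staff deciding on discharge and ICU stay after Day 7 and to the pre-unblinding data review

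*Protocol*

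**What the plan says.** Protocol 5.6 has an unblinded pharmacist apply identical labels and an opaque over-pouch, "so that the content of the bags is only known to the unblinded hospital pharmacist or designee". It also keeps the person who infuses out of most other evaluations, lets sites use covered lines, restricts code-breaking, and confines unblinded statistical work to a separate team. Protocol 9.3 expects all other study staff to stay blinded.

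The US label in Protocol 5.2.1 describes the active product: "1 mL contains: 100 mg protein of which 96% is human normal immunoglobulin". Protocol 5.4 sets a total of 2 g/kg over four days, and placebo is saline (5.1).

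Protocol 7.3.4 orders a comprehensive metabolic panel (CMP) at Screening, on Day 7, and at discharge (if after Day 7) or Day 33, and an ESR at Screening and Day 7. On location it says "All laboratory assessment will be performed at the local laboratories for each study site", then allows a central local laboratory in Russia and Ukraine. Protocol 11.1 treats all laboratory results as CRF data.

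SAP 7 states: "Decisions on missing data, identification of prohibited medications and final imputation of endpoints will be done during this blinded review phase". It adds: "Blinded data review may also include clinical evaluation of safety data for reasonableness". Under Protocol 4.5 a panel that includes sponsor staff decides, before unblinding, which subjects enter each analysis population.

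**The concern.** The physical blind can be perfect and the arm still be readable from the chart. A large protein infusion in one arm only should raise total protein and globulin, and the protocol supplies both a pre-infusion value and a Day 7 value for each subject. Protocol 7.3.2.2 also asks the investigator whether an abnormality has developed since Screening, which invites that comparison.

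Two groups of decisions follow the Day 7 result. At the site these are when to discharge and when to leave the ICU, which drive the first and fifth key secondary endpoints. At the sponsor they are the decisions listed in SAP 7 and Protocol 4.5. Prohibited medication by Day 7 counts as a primary failure (SAP 13). Later use removes a subject from the severe-progression and mortality analyses (SAP 14). If those deciding can infer the arm, bias could run in either direction.

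**Working it through.** **1. The plan's own design figure.** Protocol 9.1: "With overall two-sided significance level of 0.05 when testing the difference in proportions between two treatment groups"; "we assume 80% of subjects in the IVIG group and 60% of subjects in the placebo group will meet the primary endpoint"; "176 subjects (n=88 for each treatment group) will provide statistical power of at least 80" per cent.
- Power at 88 per arm, pooled-variance normal approximation: SE under the null = √(0.7 × 0.3 × 2/88) = 0.0691; SE under the alternative = √((0.24 + 0.16)/88) = 0.0674. Power = Φ((0.20 − 1.96 × 0.0691)/0.0674) = Φ(0.958) = 83.1%.
- Drop-out: 88/0.85 = 103.5, so 104 per arm and 208 in all.

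The figure reproduces, and nothing below changes it.

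**2. Protein load.** 2 g/kg ÷ 0.1 g/mL = 20 mL/kg. That is 140 g at an illustrative 70 kg and 250 g at the 125 kg weight limit, against 0 g with saline.

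**3. When a protein value is available.** The Day 1 to 4 panels in Protocol 7.3.4 contain no CMP or ESR. The first scheduled post-infusion CMP is on Day 7, the visit at which primary status is scored. Protocol 6.1.3 sets no order between the two.

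**4. How well protein would separate the arms.** None of these inputs is in the documents: that the CMP reports total protein and albumin, plasma volume, the share of the load in plasma on Day 7, and the SD of the change from Screening.
- Rise = 2000 mg/kg ÷ plasma volume (mL/kg) × share in plasma. This is in mg/mL; divide by 10 for g/dL.
- Correct guesses with a cut midway between the arm means = Φ(rise/(2 × SD)), assuming normal changes with equal SDs.

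| Case | Plasma volume (mL/kg) | Share in plasma | Rise (g/dL) | SD (g/dL) | Correct |
|---|---|---|---|---|---|
| Lowest | 50 | 0.20 | 0.8 | 1.0 | Φ(0.40) = 66% |
| Low | 50 | 0.40 × 0.75 = 0.30 | 1.2 | 1.0 | Φ(0.60) = 73% |
| Central | 45 | 0.45 × 0.85 = 0.38 | 1.7 | 0.8 | Φ(1.06) = 86% |
| High | 40 | 0.50 × 1.00 = 0.50 | 2.5 | 0.6 | Φ(2.08) = 98% |

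An SD of 0.5 in the high case would give 99%. A larger SD is also plausible, since Protocol 6.1.1 accepts Screening samples up to 7 days old. The midpoint cut presumes a reader who knows roughly the mean change in each arm. No figure was derived for ESR.

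**5. Which outcomes are open to influence.**
- *Day 7 status.* Entry requires supplemental oxygen and excludes invasive ventilation (Protocol 4.1), so subjects enter in category 3 or 4. Success means not worse than baseline, so a judgement between categories 1, 2 and 3 cannot change it. From baseline 4, failure needs category 5 or death. From baseline 3, the 3/4 boundary matters, and it is confirmed by A-a gradient on Day 7.
- *Day 14 status.* This follows the Day 7 CMP, and Protocol 7.2.4 schedules no A-a gradient then. Exposure is somewhat greater for subjects entering in category 3.
- *Discharge and ICU stay after Day 7.* These are clinical decisions with no such anchor.
- *Pre-unblinding decisions.* All come after the protein values exist.

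**6. Sensitivity to a shift (illustration, not an estimate).** With 104 per arm, no true effect and 60% success, suppose knowledge of the arm added 2, 5 or 10 points to the active arm. Two-sided rejection would be 6.0%, 11.5% or 32.6% instead of 5%. Nothing in the documents links correct guessing to a shift of any size. The sum applies to a proportion, not to time to discharge or ICU days.

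**The case against.** Three stronger readings are tempting, and the documents do not support them.

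- *That Protocol 5.6 blinds only the bag and label.* It also separates the infuser from most evaluations, allows covered lines, and isolates the unblinded statisticians. The gap is specific to laboratory results.
- *That the primary endpoint is compromised at the site.* Entry category, the not-worse rule, the A-a gradient and the absence of an earlier scheduled CMP leave little room. A small opening remains: the order of scoring and results is unspecified, and SAP 4.6 analyses the latest observation within the study day, so a re-score made after results arrive would be the one used.
- *That the SAP 7 reviewers are given protein values.* The SAP says only that listings follow analysis needs and that safety data may be reviewed. It does not exclude these analytes, but neither does it supply them.

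Further fair points: status imputation is largely rule-based (SAP 4.1), prohibited medications are defined by class (Protocol 4.2, SAP 13), and SAP 13 plans complete-case, worst-case and regardless-of-medication sensitivity analyses. These limit the damage but do not remove it. Whether a product was experimental still needs judgement, and population decisions follow no formula.

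Nor do the documents show that most discharges and ICU exits come after Day 7. In the pilot study cited in Protocol 1.1 (subgroup with A-a gradient above 200 mmHg), median hospital stay was 11 days with IVIG and 19 without, but median ICU stay was 2.5 and 12.5 days. Finally, Protocol 9.3 mentions a separate document on blinding the study drug, which is not among those reviewed. As described, it concerns the drug rather than laboratory data.

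**Conclusion.** The point holds as a gap in the blinding controls. One arm alone receives a large protein load, a chemistry panel is scheduled before and after it, and no section keeps the resulting values from outcome assessors or from the pre-unblinding review. If the panel reports total protein, the arm could be guessed correctly in roughly 66% to 98% of subjects (central case about 86%). That range rests wholly on assumed plasma volume, distribution, elimination and SD. It measures how readable the arm is, not bias; the bias is unquantified.

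Exposure is slight for the primary endpoint at the site. It is greater for discharge and ICU decisions after Day 7 and for the decisions under SAP 7 and Protocol 4.5. This is an inexpensive improvement, not evidence that the blind failed, and sample size and power are unaffected.

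**What to change.** 1. **SAP 7 and Protocol 4.5.** Exclude post-baseline total protein and albumin/globulin, and ESR as a precaution, from every listing used in the blinded data review until endpoint, prohibited-medication and population decisions are signed off. Creatinine, BUN, electrolytes and liver tests stay visible.
2. **Protocol 6.1.3.** Have the assessor record and sign Day 7 clinical status before viewing that day's total protein and albumin/globulin results. Safety results to the treating team should not be delayed.

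The cost is wording and a filter on listings. A restricted eCRF page is not proposed, because it would need unblinded data entry. Two limits remain. The hospital chart cannot be masked, so site protection after Day 7 is partial, and a few non-critical analytes reach the blinded team later. Because the SAP reports accelerated enrolment and a data review already held at 50% enrolled, the second change can reach only Day 7 visits still to come. The first works fully if adopted before the blinded review.
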